#### **Assessment of Prurigo Activity Score (PAS)**

The evaluation of the disease will be performed by the Investigator using the Prurigo Assessment Scale (PAS) at baseline and Week 12 using the entire scale and at week 4, 8,18 and in case of Early termination visit / Unscheduled visit, if applicable, using item 5 (number of lesions only) and 6 (excoriation/crusts and healed lesions).

PAS evaluation of the severity of at each post-treatment timepoint will be summarized as a continuous variable and as a categorical variable, given its ordinal nature by treatment group. The data will be analyzed using a Cochran-Mantel-Haenszel (CMH) test with ridit scores between nemolizumab and placebo, stratified by background of atopy (presence or absence) and country. The shift table will also be provided for overall investigator-rated evaluation change from baseline to Week 18 for each treatment group and overall.

#### **5.7.4 Other Efficacy Endpoints**

##### **Dermatology Life Quality Index (DLQI)**

DLQI will be assessed at baseline, weeks 4, 12, or early termination visit when applicable.

The DLQI score will be categorized as follows:

- 0-1 = no effect at all on subject's life
- 2-5 = small effect on subject's life
- 6-10 = moderate effect on subject's life
- 11-20 = very large effect on subject's life
- 21-30 = extremely large effect on subject's life

The DLQI can be analyzed under 6 sub-scales, namely, symptoms and feelings (question 1 and 2), daily activities (question 3 and 4), leisure (question 5 and 6), work and school (question 7), personal relationships (question 8 and 9), and treatment (question 10). For general inflammatory skin conditions, a change in DLQI score of at least 4 points is considered clinically important.

The primary study population for all QoL and productivity data will be the ITT Population. DLQI will be summarized by treatment group and visit. By-subject listings of these data should be provided.

Change from baseline in DLQI at each visit will be analyzed using ANCOVA with treatment group, baseline DLQI as a covariate, background of atopy and country as cofactors. In addition, the following analyses will be performed:

- A shift table (by visit) will be generated using the categories described above. Change from baseline in each sub-scale at each visit will be analyzed as the efficacy endpoint using ANCOVA.
- Proportion of subjects achieving a change in DLQI score of at least 4 points at each Visit up to week 12 will be analyzed using a CMH test with ridit scores between nemolizumab and placebo, stratified by background of atopy (presence or absence) and country.

Number and percentage of subjects will also be provided for the following DLQI score categories at each visit for the above categories and analyze using CMH test stratified by background of atopy and by country with the ridit scores.

#### Sleep disturbance Numeric Rating Scale (NRS)

The efficacy endpoint for the Sleep disturbance NRS will be the Absolute and Percent change from baseline in weekly average of Sleep disturbance NRS (Day 1, baseline), Week 1, Week 2, Week 4, and E/T or unscheduled visit, if applicable). These endpoints will be compared across nemolizumab and placebo treatment groups using ANOVA model for the primary analysis above separately at each assessment visit. For absolute change endpoint, the same ANOVA model, with the same factors as in the percent change model will be performed, but with baseline NRS as a covariate.

Summary statistics of objective assessment of scratching events during the night and sleep duration the two Ratios 'scratching duration/duration' and 'scratching events/duration' up to week 4 will be summarized.

A 95% CI for the treatment difference will be calculated for both absolute change and percent change of NRS from baseline and will be plotted by treatment group for ITT population.

#### 5.8 Safety Evaluation

All safety summaries and analyses will be based upon the SAF population as defined in Section 5.4.

### 5.8.1 Extent of Exposure

The extent of treatment will be summarized by treatment group as follows:

- Duration of study drug (days)
- Cumulative dose of nemolizumab (mg/kg) received
- Relative dose volume (%) of nemolizumab
- Proportion of subjects compliant with study drug at each study drug administration visit by treatment group

### 5.8.2 Adverse Events

**Analysis of severity:** The severity of each AE will be summarized as assessed by the investigator (Mild, Moderate, Severe). Within the same MedDRA PT, only the most severe AE for each subject will be counted in tabulations by severity. Within a MedDRA SOC, subjects with more than one MedDRA PT will be counted only once for the most severe AE reported. AEs for which the severity is missing will be imputed to be Severe; this imputation will take place prior to determining the most severe AE within a SOC or PT for a given subject.

**Analysis of causality:** The relationship of each AE to the study drug and/or study procedure will be summarized as assessed by the investigator (Reasonable Possibility, No Reasonable Possibility). Within the same MedDRA PT, only the AE with the highest ranked relationship to study drug and/or study procedure for each subject will be counted in tabulations by causality. Within a MedDRA SOC, subjects with more than one MedDRA PT will be counted only once for the AE that is most related to study drug and/or study procedure. AEs for which the relationship to study drug is missing will be considered as Reasonable Possibility related. The imputation for a missing relationship will take place prior to determining the most related AE within a SOC or PT for a given subject.

High-level summary of TEAEs will be presented based on 1) all causalities, 2) study drug related, and 3) study procedure (including TCS) related. The table will include the number and percentage of subjects for the following categories:

- Number of TEAEs
- Subjects with TEAEs
- Subjects with treatment-emergent SAEs (TESAEs)
- Subjects with severe TEAEs
- TEAE with fatal outcome
- Subjects temporarily discontinued from study treatment due to TEAEs
- Subjects permanently discontinued from study treatment due to TEAEs
- Subjects discontinued from study due to TEAEs

The number and percentage of subjects reporting any TEAE will be summarized by SOC and PT.

- Summary of TEAEs by MedDRA SOC and PT based on 1) all causalities; 2) study drug related, and 3) study procedure (including TCS) related
- Summary of Severe TEAEs by MedDRA SOC and PT based on 1) all causalities; 2) study drug related, and 3) study procedure (including TCS) related
- Summary of the most common TEAEs ( $\geq 5\%$ ) by MedDRA SOC and PT based on all causalities
- Summary of TEAEs by MedDRA SOC and PT based on all causalities for subgroups as described in Section 5.7.1.6

AE summaries will be ordered in terms of decreasing frequency for SOC, and PT within SOC, in the treatment group (combined, nemolizumab, then placebo), and then alphabetically for SOC, and PT within SOC. If deemed as appropriate, a different order may be applied.

All AEs will be provided in a by-subject listing which will include both the term reported on the eCRF (verbatim term) and the PT and SOC to which it is coded. Relative start and stop days will be included along with the actual onset and resolution dates. Pre-treatment AEs will be listed separately.

### 5.8.3 Deaths, Other Serious Adverse Events, and Other Significant Adverse Events

Other significant TEAEs are those TEAEs reported as leading to permanent or temporary discontinuation of study treatment, leading to discontinuation of study, AESIs.

The following summaries will be produced:

- Summary of TESAEs by MedDRA SOC and PT based on 1) all causalities; 2) study drug related, and 3) study procedure (including TCS) related
- Summary of TEAEs associated with permanent discontinuation of study treatment by MedDRA SOC and PT based on 1) all causalities; 2) study drug related, and 3) study procedure (including TCS) related
- Summary of AEs associated with discontinuation of study participation by MedDRA SOC and PT based on 1) all causalities; 2) study drug related, and 3) study procedure (including TCS) related
- Summary of AESIs based on 1) all causalities; 2) study drug related

In addition, separate listings will be provided for the following:

- Deaths and other SAEs
- Permanent discontinuations of study treatment due to AEs
- Discontinuations of study participation due to AEs
- Temporary discontinuations of study treatment due to AEs
- AESIs

#### **5.8.4 Clinical Laboratory Evaluation**

All laboratory values will be reported in SI units.

Laboratory data (absolute values and change from baseline) will be summarized descriptively by visit and treatment group.

In addition, the number and percent of subjects below, within, and above the laboratory reference ranges and the number and percentage of subjects who met criteria of PCSV (see Appendix 5) will be summarized by treatment group. Shift tables will be generated using the reference ranges. The shift will also be illustrated by the spaghetti plots.

A by-subject listing of all laboratory data will be provided by treatment group, with abnormal values flagged. Laboratory reference ranges should also be listed.

#### **5.8.5 Vital Signs, Weight, Physical Findings and Other Observations Related to Safety**

##### **5.8.5.1 Vital Signs and Weight**

All vital signs and weight data (absolute values and change from baseline) will be summarized by visit and treatment group.

In addition, the number and percent of subjects with blood pressure (systolic and diastolic), pulse rate, and weight values meeting criteria for PCSV will be summarized by treatment group.

A by-subject listing of vital signs data will be provided, with potentially clinically significant values flagged.

##### **5.8.5.2 Peak Expiratory Flow (PEF)**

For subject with medical history of asthma, PEF measurements (absolute values and change from baseline for actual PEF and %predicted PEF) will be summarized by visit and treatment group.

Number and percentage of subjects who met the following criteria will be summarized.

- With %predicted PEF less than 80%
- With  $\geq 20\%$  change (decrease) from baseline in PEF

A by-subject listing of respiratory assessments/PEF will be provided.

#### 5.8.5.3 Electrocardiogram

A by-subject listing of ECG overall interpretation will be provided.

### 5.9 Pharmacokinetic and Pharmacodynamics Evaluations

#### 5.9.1 Pharmacokinetic Parameter Calculation Methods

Derivation of PK parameters will be the responsibility of Quantitative Clinical Development (QCD), PAREXEL International. PK parameters will be calculated by non-compartmental analysis methods from the concentration-time data using Phoenix® WinNonlin® (WNL) Professional (Version 6.3 or higher). The following guidelines will be applied:

- Actual sampling times relative to dosing will be used in the calculation of all derived PK parameters. If the dosing time is not available for the calculation of actual sample time or the sample collection time is not available, the nominal time as recorded in the database will be used in the calculation. The listing of serum concentrations will note any instance in which a nominal time is presented in place of an actual sample time.
- BLQs at the beginning of a subject profile (i.e., before the first incidence of a measurable concentration) will be assigned to zero.
- BLQs at the end of a subject profile (i.e., after the last incidence of a measurable concentration) will be set to missing.
- Single BLQs which fall between two measurable concentrations will be set to missing.
- Consecutive BLQs which fall between measurable concentrations will be set to missing.
- Data from subjects with missing concentration values (missing samples) may be used if pharmacokinetic parameters can be estimated using the remaining data points.

Derivation of the pharmacokinetic parameters for nemolizumab will be performed using the following guidelines:

- $C_{max}$  will be obtained directly from the concentration-time data.
- $T_{max}$  is the time at which  $C_{max}$  is observed.
- $T_{last}$  is the time of the last quantifiable concentration.
- $\lambda_z$  will be estimated at terminal phase by linear regression after log-transformation of the concentrations:
  - Only those data points that are judged to describe the terminal log-linear decline will be used in the regression.
  - A minimum number of three data points in the terminal phase will be used in calculating  $\lambda_z$  with the line of regression starting at any post- $C_{max}$  data point ( $C_{max}$  should not be part of the regression slope). The adjusted correlation coefficient ( $R^2$  adjusted) in general should be greater than 0.80. Any value < 0.80 will be excluded from the analysis.
  - The interval used to determine  $\lambda_z$  should be equal or greater than 1.5-fold the estimated half-life or otherwise flagged and excluded from the analysis.
- $t_{1/2}$  will be calculated as  $\ln 2 / \lambda_z$ .
- AUC is calculated by the linear up/log down method (linear method will be employed for all incremental trapezoids arising from increasing concentrations and the logarithmic method will be used for those arising from decreasing concentrations).

$$AUC_{0-t} = \int_0^t C(t) dt$$

$$AUC_{0-\infty} = \int_0^t C(t) dt + \int_t^{\infty} C(t) dt = AUC_{0-t} + C_t / \lambda_z$$

- $C_{last}$  is the last observed quantifiable concentration.
- %AUCex will be calculated as  $(1 - [AUC_{0-t}/AUC_{0-\infty}]) \times 100$ . The %AUCex should not exceed 20% for each individual profile. If the %AUCex is more than 20%, the individual result should be flagged and mentioned in the report as well as all parameters depending on AUC0- $\infty$ . If the %AUCex is greater than 30%, the value and all dependent parameters may be flagged and excluded, at the discretion of the PK scientist.

When appropriate, the following PK parameters will be determined for each subject:

From baseline to week 4:

- $C_{max}$ : The observed peak drug concentration

- $T_{max}$ : The time at which  $C_{max}$  occurs
- $T_{last}$ : Time of last quantifiable concentration
- $AUC_{0-4W}$ : Area under the concentration time curve from pre dose through 28 (4 weeks) days post dosing.  $AUC_{0-4W}$  will be calculated by mixed linear logarithmic trapezoidal method

From baseline to week 12:

- $AUC_{0-12W}$ : Area under the concentration time curve from pre dose through 12 weeks post dosing.  $AUC_{0-12W}$  will be calculated by mixed linear logarithmic trapezoidal method.  $AUC_{0-12W}$  included the serum drug concentration up to week 12 (i.e. the serum concentration collected at baseline, week 1, 2, 4, 8 and 12)

From baseline to week 18:

- $AUC_{0-18W}$ : Area under the concentration time curve from pre dose through 24 weeks post dosing.  $AUC_{0-18W}$  will be calculated by mixed linear logarithmic trapezoidal method.  $AUC_{0-18W}$  included the serum drug concentration up to week 18 (i.e. the serum concentration collected at baseline, week 1, 2, 4, 8, 12, 16 and 18)
- From baseline to week 18 (Early termination or Unscheduled visit, if applicable)
  - $AUC_{0-t}$ : area under the concentration time curve calculated by the mixed linear logarithmic trapezoidal method from  $T_0$  up to the sampling time corresponding to the last quantifiable concentration ( $C_{last}$ )

From week 12 to week 18 (or Early termination or Unscheduled visit, if applicable):

- $t_{1/2}$ : the terminal half-life value ( $t_{1/2}$ ) will be calculated using the equation  $\ln 2/k$  after the last drug injection (week 8).
- $AUC_{0-t}$ : area under the concentration time curve calculated by the mixed linear logarithmic trapezoidal method from  $T_0$  up to the sampling time corresponding to the last quantifiable concentration ( $C_{last}$ ).
- $AUC_{0-\infty}$ : Area under the plasma concentration-time curve calculated by the mixed linear logarithmic trapezoidal method from  $T_0$  and extrapolated to time infinity as:  $AUC_{0-\infty} = AUC_{0-t} + C_{last} / k_{el}$ . When the extrapolation represents more than 20%,  $AUC_{0-\infty}$  and  $t_{1/2}$  will not be reported.

At weeks 4, 8, 12, 16, 18 (or Early termination or Unscheduled visit if applicable):

- $C_{trough}$ : The residual drug concentration
- Accumulation index: calculated with the serum nemolizumab trough concentration obtained 4 weeks after the first dose (week 4) and 4 weeks after last drug injection (week 18).

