7.3.1 Technical procedures for pharmacokinetic blood sampling

At each sampling time for PK assessment, 2 mL of blood will be collected for the assessment of nemolizumab concentrations in serum samples.

For ADA assessment, 2 mL of blood will be collected at the same time as PK sampling.

PK samples are to be collected before drug injection (pre-dose samples) at Baseline, weeks 4, 8; the maximum allowed time windows for PK blood sampling is 30 minutes before drug injection. At weeks 1, 2, 12, 16 and 18 blood samples will be collected at the corresponding usual time of drug injection with an allowed time window of ± 1 h.

The date and time of collection for each sample along with the time of the last study drug injection and missed injections have to be recorded on the eCRF.

Processing of blood samples for PK and ADA assessments will be described in a specific manual.

Volumes of blood to be obtained for PK, ADA tests are summarized in [Appendix 1](#).

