8.1.2.4 Visit 8 / Day 85, Week 12 (+/- 5 days)

The Investigator or designee will:

1. Collect information regarding AE (including review of laboratory values) and concomitant therapies/procedures.
2. Perform physical examination (including weight) & vital signs measurements.
3. Collect blood samples for hematology & entire biochemistry.
4. Collect urine to perform urinalysis test.
5. Complete urine pregnancy test for female of childbearing potential only.
6. Conduct respiratory medical assessments, including PEF for subjects with a history of asthma.
7. Check subject's record for pruritus NRS and VRS and remind subject to complete them daily
8. Ask subject to complete the DLQI.
9. Complete the evaluation of PAS and IGA.
10. Collect blood samples for PK, ADA & biomarkers.
11. Perform D Squames.
12. Perform 4-mm biopsies for subjects who consented.
13. Take whole body photographs when applicable.
14. Schedule the next visit for Visit 9.

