8.1.3 Follow up period

8.1.3.1 Visit 9 / Day 113, Week 16 (+/- 5 days)

The Investigator or designee will:

1. Collect information regarding AE (including review of laboratory values) and concomitant therapies/procedures.
2. Perform vital signs measurements.
3. Complete urine pregnancy test for female of childbearing potential only.
4. Conduct respiratory medical assessments, including PEF for subjects with a history of asthma.
5. Collect blood samples for PK, ADA
6. Control the good healing of biopsies when applicable.
7. Check subject's record for pruritus NRS and VRS and remind subject to complete them daily
8. Schedule the next visit for Visit 10.

8.1.3.2 *Visit 10 / Day 126, Week 18 (+/- 7 days)*

The Investigator or designee will:

1. Collect information regarding AE (including review of laboratory values) and concomitant therapies/procedures.
2. Check subject's record for pruritus NRS and VRS.
3. Perform physical examination & vital signs measurements.
4. Complete urine pregnancy test for female of childbearing potential only.
5. Conduct respiratory medical assessments, including PEF for subjects with a history of asthma.
6. Complete the evaluation of PAS and IGA.
7. Collect blood samples for PK, ADA
8. Take whole body photographs (selected centers only).
9. Collect the device used for Pruritus assessments
10. Complete the exit form.

8.1.4 *Early Termination visit or unscheduled visit:*

The Investigator or designee will:

1. Collect information regarding AE (including review of laboratory values) and concomitant therapies/procedures.
2. Check subject's record for pruritus NRS and VRS.
3. Ask subject to complete the DLQI.

4. Complete the evaluation of PAS and IGA.
5. Perform physical examination & vital signs measurements and ECG.
6. Conduct respiratory medical assessments, including PEF for subjects with a history of asthma.
7. Complete urinalysis.
8. Complete urine pregnancy test for female of childbearing potential only.
9. Collect blood samples for hematology & biochemistry
10. Collect blood samples for PK and ADA.
11. Complete the exit form in case of early termination and collect e-devices.

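### SAP 5.9.1 falls back to nominal sampling time even when the calendar date is recorded, which can move an affected subject's half-life from 14 to about 12–17 days, or about 11–20 days at worst

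*SAP*

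**What the plan says.** SAP 5.9.1 bases all derived PK parameters on actual sampling times relative to dosing. The exception reads: "If the dosing time is not available for the calculation of actual sample time or the sample collection time is not available", then "the nominal time as recorded in the database will be used in the calculation". Disclosure is by listing: "The listing of serum concentrations will note any instance in which a nominal time is presented in place of an actual sample time". The SAP gives no separate rule for a sample whose date is known and whose clock time is not.

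Protocol 7.3.1 requires the eCRF to hold "The date and time of collection for each sample along with the time of the last study drug injection and missed injections". It also fixes the time of day: at Weeks 1, 2, 12, 16 and 18 samples are to be "collected at the corresponding usual time of drug injection with an allowed time window of ± 1 h".

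The visit windows are much wider. They are Day 85 ± 5 days (Protocol 8.1.2.4), Day 113 ± 5 days (8.1.3.1) and Day 126 ± 7 days (8.1.3.2).

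SAP 5.9.1 estimates the half-life after the Week 8 injection from Weeks 12 to 18, where three samples are scheduled. The terminal regression needs at least three points, an adjusted R-squared of at least 0.80, and an interval of at least 1.5 estimated half-lives.

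**The concern.** A missing clock time leaves less than a day of uncertainty, and about an hour if the protocol's sampling time was kept. The rule answers this by discarding the date as well, so the time used can be wrong by up to 7 days, which is half a half-life. Only three scheduled points carry the terminal slope, so each has strong leverage. The distorted points can still lie close to a straight line on the log scale, so the quality checks need not flag the profile. What is at stake is the half-life reported for an affected subject and, to a lesser degree, the extrapolated part of AUC0-∞.

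**Working it through.** **Inputs.** True half-life 14 days: Protocol 1.3 gives around 2 weeks, and SAP 4.1 equates 10 weeks with 5 half-lives, so 70/5 = 14, which agrees. Nominal days x = 85, 113, 126, with windows of ±5, ±5 and ±7 days. Nominal time is taken to mean the planned visit day. The decline is log-linear without assay error.

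**Formula, all three samples at nominal time.** The mean of x is 108 and the deviations are −23, 5 and 18, so Sxx = 529 + 25 + 324 = 878. With e = actual minus nominal day,

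estimated half-life = 14 / [1 + Σ(x − 108)e / 878].

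A shift common to all three times (such as the day of the Week 8 injection) cancels out.

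- Actual days 90, 108, 119: Σ = −115 − 25 − 126 = −266, so 14/0.697 = 20.1 days.
- Actual days 80, 118, 133: Σ = +266, so 14/1.303 = 10.7 days.
- Only the Week 18 visit off schedule (Day 119 or 133): Σ = ∓126, so 14/0.856 = 16.3 or 14/1.144 = 12.2 days.
- Visit days uniform over the windows (an assumption): central 95% range 11.5–17.8 days if continuous, 11.4–18.3 in whole days.
- Nominal times counted in weeks (84, 112, 126 days) instead: extremes 11.0 and 20.5 days.

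**One sample at nominal time, the other two at actual time.** For Week 18 with the others at Days 90 and 108, x = 90, 108, 126 and Sxx = 324 + 0 + 324 = 648. Then Σ = ±18 × 7 = ±126, giving 14/1.194 = 11.7 or 14/0.806 = 17.4 days. The same search over the windows gives:

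| Sample at nominal time | Estimated half-life, days |
|---|---|
| Week 12 only | 12.1–16.6 |
| Week 16 only | 13.2–14.9 |
| Week 18 only | 11.7–17.4 |

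**SAP checks.** Adjusted R-squared is 0.997 at the 10.7-day extreme and 0.990 at the 20.1-day extreme. With all three samples at nominal time it does not fall below 0.82 anywhere in the windows. The nominal interval is 126 − 85 = 41 days, against 1.5 × 20.08 = 30.1 required. Among the patterns with one, two or three nominal times, the 0.80 limit is missed only in a corner case with Weeks 16 and 18 both nominal (0.785).

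**AUC0-∞.** In an illustrative three-dose one-compartment model (assumed absorption half-life 1–3 days, T0 at the first dose), the two extremes change AUC0-∞ by about +3% and −1%, because only about 1–5% of it is extrapolated.

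**Group summary.** With continuous uniform visit days, the SD of the relative slope error is √[(529·25/3 + 25·25/3 + 324·49/3)]/878 = 0.113. If 4 of 35 subjects had all three times nominal, the geometric mean would vary by about ±1.96 × 0.113 × √4/35 = ±1.3%, or 13.8–14.2 days. If all 35 were affected, simulation gives 13.6–14.6 days.

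**After the change.** An error of ±1 h in each sample gives Σ = ±46/24 = ±1.92, so 13.97–14.03 days. Even ±12 h gives Σ = ±23, so 13.6–14.4 days.

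**The case against.** The case on the other side is substantial, and much of it stands.

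- **The trigger may be rare.** Protocol 7.3.1 requires dates and times, and Protocol 10.3 provides edit checks until queries are resolved. The eCRF is not among the documents, so it cannot be confirmed that a date can be stored without a time. This stands as a limit on frequency. It does not defend what the rule does once a time stays missing.
- **A reader might infer that half-lives in this trial will generally come out anywhere from 11 to 20 days.** The documents do not support that. The range needs three nominal times in one subject and visits at opposite window ends.
- **A reader might infer that one missing Week 8 injection time always moves all three terminal samples to nominal time.** That follows only if times are counted from that injection. SAP 5.9.1 does not say which dose is meant, and AUC0-12W and AUC0-18W start before the first dose.
- **A reader might infer that AUC0-∞ and the group results are materially wrong.** The calculations above point to small effects. SAP 5.9.2 does not list half-life among the parameters given a geometric mean and CV.
- **The plan may withhold the upper extreme.** If T0 for the Week 12–18 AUC means Week 12, the 20.1-day case extrapolates 23%, above the 20% at which SAP 5.9.1 says half-life is not reported. With T0 at the first dose it is about 5% and the value is reported. The SAP does not settle which applies.
- **The listing shows each substitution.** It does, but the substituted time still enters the calculation.

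**Conclusion.** The point holds as a minor one. For a subject with known dates, the rule replaces a time that can be recovered to within hours by one that may be off by 5 to 7 days. One affected sample can give about 12–17 days for a true 14, and the worst case is about 11–20 days. The SAP's checks would generally not detect it. This rests on a 14-day log-linear decline without assay error, visits within their windows, and nominal time meaning the planned visit day. How many subjects would be affected is not stated, so the total effect cannot be sized. No efficacy or safety comparison depends on it.

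**What to change.** Revise the exception in SAP 5.9.1. Where the dates of injection and sample are known, calculate with those dates and impute only the missing clock time, using the usual injection time to which Protocol 7.3.1 ties sampling. Use nominal time only when the date itself is missing. Also state which dose the sampling times are counted from.

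Continue to flag nominal-time samples in the listing, and do not exclude them automatically from the terminal regression. Only three samples are scheduled after the last injection and three are required. Exclusion would therefore usually remove that subject's half-life and AUC0-∞ unless an unscheduled or early-termination sample exists. The price of keeping them is that samples without a date retain the error described here, visibly flagged.

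The cost is a sentence or two in the SAP and a check that the database holds date and time as separate fields. No new data are needed.

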#### Pharmacokinetics (PK)

- Characterization of nemolizumab PK profile and exposure response relationship in patients with PN

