## 4 INVESTIGATIONAL PLAN

### 4.1 Overall Study Design and Plan

This is a randomized, placebo-controlled, double-blinded, parallel group, multicenter study to evaluate the safety and efficacy of nemolizumab in patients suffering from PN. Approximately 70 adult patients suffering from PN for at least 6 months with severe pruritus defined by the mean of the worst daily intensity of the NRS score  $\geq 7$  over the previous week at baseline will be randomized in the study. Subjects meeting inclusion/exclusion criteria will be randomized in a 1:1 ratio to nemolizumab or placebo. Each subject will receive three subcutaneous injections of 0.5mg/kg of nemolizumab or matching placebo. Injections will be administered every 4 weeks (at baseline, week 4 & week 8).

Subjects' participation in the study will be up to 22 weeks, including an up to 4-week screening period, a 12-week treatment period (last study drug injection at week 8) and a 6-week follow-up period (10 weeks after the last study drug injection corresponding to 5 half-lives of nemolizumab).

Assessments of efficacy, safety, PK, PD, and biophysical will be conducted throughout this clinical trial. Refer to Appendix 1 for the complete schedule of assessments.

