#### **4.2.4 Pharmacokinetic and Anti-drug Antibody Assessments**

Blood samples will be collected to determine the PK profile of nemolizumab and to assess anti-drug antibodies (ADA). The serum concentration of nemolizumab will be assessed at baseline, weeks 1, 2, 4, 8, 12, 16, 18, and in case of early termination or unscheduled visit for safety reasons. ADA will be assessed at baseline, weeks 4, 8, 12, 16 and 18, and in case of early termination or unscheduled visit for safety reason.

Results will be described in the bioanalytical report, which will be included as an appendix in the final clinical study report.

Nemolizumab serum concentrations will be determined using validated ELISA method by a sponsor representative. A bioanalytical plan describing the details of the bioanalytical work related to serum samples of nemolizumab assessment will be written before the beginning of the sample analysis.

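### The cumulative AUCs in SAP 5.9.1 are trapezoids drawn across two dosing intervals with no samples inside them, so they come out roughly 27–46% too low at a two-week half-life

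*SAP*

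**What the plan says.** - **Dosing** (SAP 4.1): "Injections will be administered every 4 weeks (at baseline, week 4 & week 8").
- **Sampling** (SAP 4.2.4): "The serum concentration of nemolizumab will be assessed at baseline, weeks 1, 2, 4, 8, 12, 16, 18", plus early-termination and unscheduled safety visits.
- **Timing of the samples on dosing days** (Protocol 7.3.1): "PK samples are to be collected before drug injection (pre-dose samples) at Baseline, weeks 4, 8", at most 30 minutes before the injection.
- **Parameters** (SAP 5.9.1): AUC0-12W "included the serum drug concentration up to week 12 (i.e. the serum concentration collected at baseline, week 1, 2, 4, 8 and 12"). AUC0-18W uses "the serum concentration collected at baseline, week 1, 2, 4, 8, 12, 16 and 18", yet the same bullet describes it as "Area under the concentration time curve from pre dose through 24 weeks post dosing". AUC0-t and AUC0-infinity are also listed, running from a T0 that is not defined, in a block for Weeks 12 to 18.
- **Rule** (SAP 5.9.1): "AUC is calculated by the linear up/log down method".
- **Role**: SAP 5.9.2 treats the non-compartmental parameters as primary PK endpoints. The PK objective is "Characterization of nemolizumab PK profile and exposure response relationship in patients with PN".

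The supplied protocol (7.3.2) lists AUC0-t for baseline to Week 4, and AUC0-t and AUC0-infinity for Weeks 12 to 18. It does not list AUC0-12W or AUC0-18W.

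**The concern.** A trapezoid estimates exposure only if the samples follow the curve. After the first injection there are samples at Weeks 1 and 2. After the second and third, the next scheduled sample is four weeks later. The segment from Week 4 to Week 8, and the one from Week 8 to Week 12, joins two troughs and leaves out the rise and fall caused by the injection at its start. Nothing in SAP 5.9.1 corrects for this or warns of it.

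The error always goes the same way, and its size depends on each subject's absorption and elimination. The reported cumulative exposures would be too low by an amount that no single factor can restore.

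**Working it through.** **Inputs from the documents.** Equal doses at Weeks 0, 4 and 8. Samples at Weeks 0, 1, 2, 4, 8, 12, 16 and 18. Linear-up/log-down rule. Half-life about 2 weeks and dose-proportional kinetics (Protocol 1.3), so single-dose profiles may be added.

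**Assumed.** One compartment with first-order absorption. Tmax is not in the documents and is varied from 1 to 10 days.

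**Plan's own figure.** 10 weeks of follow-up / 2 weeks = 5 half-lives, as the SAP states.

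**Formulas** (time in weeks, concentration in units of bioavailable dose/volume)

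- ke = ln 2 / half-life = 0.6931/2 = 0.3466
- ka solves Tmax = ln(ka/ke)/(ka − ke); for Tmax = 5 days (0.714 weeks), ka = 3.638
- C1(t) = ka/(ka − ke) × [exp(−ke·t) − exp(−ka·t)]; C(t) = C1(t) + C1(t−4) + C1(t−8)
- Rising segment: Δt(a + b)/2. Falling segment: Δt(a − b)/ln(a/b)

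**Worked case, Tmax 5 days.** Model concentrations at Weeks 1, 2, 4, 8, 12, 16 and 18: 0.752, 0.552, 0.276, 0.345, 0.363, 0.091, 0.045.

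| Interval | Trapezoid | Model AUC | Shortfall |
|---|---|---|---|
| Weeks 0–4 | 1.820 | 2.088 | 12.8% |
| Weeks 4–8 | 4 × (0.2763 + 0.3454)/2 = 1.243 | 2.686 | 53.7% |
| Weeks 8–12 | 4 × (0.3454 + 0.3627)/2 = 1.416 | 2.836 | 50.1% |
| AUC0-12W | 4.480 | 7.610 | 41.1% |
| AUC0-18W | 5.395 | 8.525 | 36.7% |
| AUC0-infinity | 5.395 + 0.0453/0.3466 = 5.526 | 3/0.3466 = 8.656 | 36.2% |

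The unsampled Weeks 4–12 account for (2.686 − 1.243) + (2.836 − 1.416) = 2.863, which is 37.6% of 7.610. The other 3.5 percentage points come from sparse sampling after dose 1.

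**Shortfall (%) by assumed Tmax, half-life 2 weeks**

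| Tmax (days) | AUC0-4W | AUC0-12W | of which Weeks 4–12 | AUC0-18W | AUC0-infinity |
|---|---|---|---|---|---|
| 1 | 21.6 | 46.4 | 40.4 | 41.9 | 41.3 |
| 3 | 17.7 | 44.2 | 39.3 | 39.7 | 39.1 |
| 5 | 12.8 | 41.1 | 37.6 | 36.7 | 36.2 |
| 7 | 9.3 | 37.6 | 35.1 | 33.3 | 32.8 |
| 10 | 6.9 | 31.6 | 29.9 | 27.4 | 26.9 |

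**Half-life.** At Tmax 5 days, AUC0-12W is about 48% low for a 10-day half-life, 41% for 14 days and 37% for 18 days.

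**Meaning of T0.** If T0 is the Week 8 injection instead of the first dose, AUC0-infinity is still about 26–41% low over Tmax 1–10 days.

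**Do the SAP's checks catch it?** In the worked case the extrapolated part is 0.131/5.526 = 2.4%, against a limit of 20%. The terminal slope from Weeks 12–18 spans 6/2 = 3.0 half-lives, against a minimum of 1.5. Both checks pass.

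**The case against.** The strongest reply is that little hangs on these numbers. SAP 5.9.2 plans geometric means and between-subject variation only for AUC0-28d (the same quantity as AUC0-4W), trough concentrations and Cmax. It relates concentrations, not these AUCs, to itch by PK/PD modelling. That is correct, and it rules out several inferences a reader might draw:

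- **Repeated dosing seems to lower exposure.** At Tmax 3–7 days AUC0-12W/AUC0-4W would compute as 2.4–2.6 instead of 3.6–3.7. But no such ratio is planned, and the accumulation index uses trough concentrations.
- **Anti-drug antibody comparisons are distorted.** The SAP plots individual profiles with and without antibodies; it plans no AUC comparison.
- **Subjects are ranked wrongly.** If only the half-life varies (10, 14, 18 days; Tmax 5 days), model AUC0-12W is 5.77, 7.61, 9.16 and computed AUC0-12W is 2.98, 4.48, 5.82. The order holds. Reordering would need further assumptions.

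A second reply is that the size rests on an absorption rate the documents do not give. That stands as a limit on the size, not on the direction: the values are too low whenever an injection lifts the concentration above the line between neighbouring troughs.

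A third is that SAP 5.9.1 derives parameters only where appropriate and that modelling is foreseen. Neither helps as written. No criterion concerns an unsampled dosing interval, and the modelling is exploratory and does not replace these AUCs.

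The 24-week wording is a drafting slip that the sample list in the same bullet resolves. It adds nothing to the bias.

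**Conclusion.** The point holds for AUC0-12W, AUC0-18W, and AUC0-t and AUC0-infinity beyond Week 4. Followed as written, SAP 5.9.1 gives values that are systematically too low and pass its own checks. With a 2-week half-life, one-compartment linear kinetics and an assumed Tmax of 1–10 days, the shortfall is about 32–46% for AUC0-12W and 27–42% for AUC0-18W and AUC0-infinity. Most of it comes from Weeks 4–12; the rest is the first interval, where AUC0-4W is itself about 7–22% low. Because the bias grows as the half-life shortens, no constant correction works.

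A reader might put the loss at half for all three AUCs. At the documented half-life none reaches 50%; losses of that size appear only within the single unsampled intervals, or for AUC0-12W at shorter half-lives.

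The parameters belong to a group the SAP calls primary for PK, so they should be corrected. The efficacy conclusions are untouched.

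**What to change.** 1. Remove AUC0-12W and AUC0-18W as trapezoid parameters.
2. Restrict non-compartmental AUC0-t to the first dosing interval, as in the baseline-to-Week-4 list of Protocol 7.3.2.
3. Keep AUC0-4W, observed Cmax and Tmax, trough concentrations and terminal half-life. State that the first post-dose sample is on Day 7, so an earlier peak cannot be seen (at Tmax 3 days, observed Cmax is 0.741 against 0.862, 14% low).
4. If cumulative AUC or AUC0-infinity is wanted, derive it from a PK model fitted to all samples with actual dose times. Superposition of the first-interval profile is the alternative, with its residual bias stated: at that sampling density AUC0-12W would still be about 5–18% low over Tmax 1–10 days.
5. Define T0, reconcile AUC0-infinity and the later AUC0-t with Protocol 7.3.2, and correct 24 weeks to 18 weeks for any AUC0-18W that is kept.

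**Cost.** SAP wording, a small amount of PK modelling, and a documented change from the protocol's parameter list for AUC0-t and AUC0-infinity. AUC0-12W and AUC0-18W are not in the supplied protocol's list, so dropping them contradicts nothing there. Cumulative exposure becomes model-based. No new samples are required.
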